 158 (*immunofluorescence images*).¹⁸

177 In the upper quadrants (A), the immunofluorescence images (starting from the left) show definite higher signal in GLP-1R antibody-
 178 treated EAT, irrespective of diabetes, when compared to GLP-1R antibody-treated SAT and to not treated with primary antibody EAT
 179 (last image on the right). Lower quadrants (B) images show the amplification of the GLP-1R signal using biotinylated anti mouse IgG,
 180 horseradish peroxidase-streptavidin and alexa fluor 647 tyramide. DAPI was used to label the nucleus and autofluorescence of the tissue
 181 was collected at 488nm excitation.

182

183 So, for the first time, we found that human EAT express GLP-1R. GLP-1A effects may be
 184 therefore visceral fat specific and target EAT. However, the mechanisms mediating the
 185 actions of GLP-1 analogues on adipose tissue are still unclear. Liraglutide may improve
 186 EAT insulin sensitivity and microcirculation, stimulate EAT thermogenesis and adipocyte
 187 browning.¹⁹⁻²²

188 **Short term effects of Liraglutide on inflammation**

189 The experimental study by Shiraki et al showed a rapid effects of liraglutide in reducing
190 TNF- α -induced oxidative stress and inflammation in endothelial cells (25). A rapid anti-
191 inflammatory effects of liraglutide on endothelial cells was also reported by Krasner et al
192 Liraglutide reduced the inflammatory responses to TNF α and LPS stimulation, with a
193 significant reduction of protein expression of the adhesion molecules VCAM-1 and E-
194 Selectin, and THP-1 monocyte adhesion in cultured human aortic endothelial cells (26).
195 Additionally, we provided evidence that epicardial fat expresses the GLP-1R protein and
196 mRNA, such as the heart. Hence, liraglutide is more likely to have a direct effect on
197 epicardial fat transcriptome than mediated by weight loss or glycemic control.
198 The LEAD trials showed a decrease in mean weight ranging from 1 to 3.2 kg (2.2 to 7.04
199 pounds) over the course of 26 or 52 weeks with liraglutide.

200

201 **Significance** We believe that this study proposal may have a great relevance and impact
202 in the research and clinical management of CAD. From a pathophysiological perspective,
203 this study proposal can provide data that will contribute the understanding of the complex
204 mechanisms that lead to the development and progression of CAD. Understanding whether

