205 EAT plays a metabolic role in CAD is key. This study can provide evidences of the recently
206 suggested cardioprotective mechanisms of Liraglutide. Treatment with Liraglutide and
207 other GLP1-A may reduce EAT inflammation and revert EAT to its physiological function
208 and therefore to a cardioprotective role. From a clinical perspective, this study proposal
209 can provide data that will open new avenues and have an important impact in the
210 management of CAD. Liraglutide may become an effective treatment of patients with CAD
211 and diabetic cardiovascular complications. EAT can be easily measured, as we first
212 developed, and then targeted by Liraglutide, other GLP-1A or other anti-inflammatory
213 drugs in patients with CAD.

214 **Innovation** This proposal contains a number of novel concepts with important clinical
215 applications. For the first time this project will evaluate the idea that GLP-1 activation may
216 reduce EAT inflammation in subjects with T2DM and CAD. This is will be the first time
217 that liraglutide effects will be evaluated on EAT samples obtained from subjects with
218 T2DM and CAD. These important points will be addressed in well-studied population of
219 subjects, as was never done before. Based on pre-existing data, the expected liraglutide
220 effects on the epicardial adipose tissue inflammatory genes, primary endpoint, may not
221 necessarily be time dependent. The shorter term of treatment that may occur in some
222 patients may actually rule out the potential confounding effect of the liraglutide-associated
223 weight loss on the study outcomes

224

225 **Study Rationale** Liraglutide, may have properties that go beyond the glucose-lowering
226 effects, as the recent LEADER trial showed that Liraglutide reduces the risk of major
227 cardiovascular events. Hence, our timely proposal will help the understanding of the

228 mechanisms of the cardio-protective effects of Liraglutide. As our preliminary data are
229 showing that a) EAT is highly inflammatory fat depot affecting the coronary arteries, b)
230 Liraglutide causes a massive and rapid reduction of EAT thickness, c) EAT expresses GLP-
231 1R our hypotheses can be likely proven in this study. Our proposal would provide stronger
232 evidences for using GLP-1As in the treatment of CAD. In addition, as EAT is an easily
233 measurable and modifiable risk factor, as we first developed, it can be targeted by

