602 those patients who will receive treatment only for 3 weeks. The difference in EAT TNF- α
603 and IL-6 between liraglutide treated and placebo treated patients is expected to be
604 approximately 1X fold after 3 weeks of treatment.

605

606 The larger sample proposed in this current project would likely reduce the variability. To
607 further assure consistency of results, mRNA and protein expression values will be log-

608 transformed prior to statistical analyses unless they will be normally distributed.
 609 Housekeeping genes will be also used for both RT-PCR and western blot analyses.
 610 In those patients who will not complete the 12-week treatment, the analysis of EAT genes
 611 from the samples will be time adjusted

612
 613 Statistical power was also calculated to detect statistically significant differences in the
 614 ultrasound measured EAT thickness, secondary endpoint, between the two study arms Our
 615 group very recently showed that additional therapy with liraglutide for 12 weeks caused a
 616 reduction in ultrasound measured EAT from 9.6 ± 2 to 6.2 ± 1.5 mm ($p < 0.001$) in 54 patients
 617 with T2DM ¹¹. Given the reference value and the expected difference in EAT, the
 618 statistical power of the study (two-sided, $\alpha = 0.05$) was calculated.

619

Outcome	Reference value \pm SD	Expected Difference	Detectable difference with 80% power $\alpha = 0.05$	Detectable difference with >99% power $\alpha = 0.05$
EAT (mm)	9.6 ± 2	-20-or -30%	-20% (absolute difference = 1.9)	-30% (absolute difference = 2.88)

620

621 Assuming a difference of approximately 2 mm (20%) in EAT to be clinically significant
 622 (based on our recent and previously published data ¹⁰⁻¹⁴), a convenience sample of 20
 623 individuals for each group will therefore provide at least the statistical power (80%) to
 624 detect an expected difference of at least -20% in the EAT before and after treatment with
 625 liraglutide. Baseline standard Deviation (SDs) of 2 is expected to lower to approximately
 626 1.5 for the expected change. The expected change of SD will further assure significant
 627 statistical power of the comparative test.

628

629 In those study patients who will not be able to complete the 12-week treatment, we
 630 anticipate to see a 15% of EAT reduction after 3 weeks in patients who will be allocated to
 631 liraglutide. This anticipated 15% of EAT reduction will remain clinically significant. For

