 632 example, a EAT thickness of 10 mm may likely decrease to 8.5 mm after 3 weeks of
 633 treatment with liraglutide, a clinically meaningful change for the patient cardio-metabolic
 634 profile.

635

636 This sample size also considers the difficulties with recruitment in the real world clinics.
 637 Based on our previous studies in humans, some participants may be lost to follow-up.

638

639 Student's t-test or non-parametric (Mann-Whitney) tests, depending on whether the genes
 640 mRNA expression and protein present or not a normal distribution, will be used to compare
 641 the effects of treatment (liraglutide versus placebo) on the variables measured. Student's
 642 t-test will be also used to compare ultrasound measured EAT thickness before and after
 643 treatments. Continuous variables will be considered as age-adjusted, sex-adjusted and
 644 weight-adjusted means with their SDs or median, if values are skewed.

645 Univariate regression models will be performed to assess the correlation between clinical
646 variables, including echocardiographic EAT thickness and blood tests, and EAT gene and
647 protein expression. Two-tailed $p < 0.05$ indicates statistical significance.

648

649 **Data Handling and Record Keeping**

650 Each of the dedicated clinic exam rooms provides direct access to the clinical research
651 study electronic data capture (EDC) eVelos system provided by the Clinical Research
652 Informatics and Data Management Unit of the Center for Health Informatics and
653 Bioinformatics at University of Miami (UM). The investigator and research coordinator
654 will collect and manage the data.

655 Data collection records with personal identifiers will be stored in locked file cabinets, at
656 [name]. Blood samples drawn
657 and stored in conjunction with this study will not be labeled with information that could
658 directly identify study subjects. Presentation of the study results at scientific meetings or
659 in publications will not identify subjects. Access to research and confidential records will
660 be limited to clinical investigators, research coordinators, and the IRB at UM.

661 **Adipose tissue samples storing**

662 Each adipose tissue sample will be snap frozen in liquid nitrogen and stored at -80°C until
663 analysis in a freezer, in [name] lab, University of Miami, Dept of Microbiology, 1600

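### Adjusted means are promised but the arms are compared by an unadjusted test chosen on observed normality, and the weight used for adjustment has no stated time point

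*Combined protocol and SAP*

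**What the plan says.** All the analysis wording is in Statistical Considerations of the combined protocol and SAP.

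- **Treatment comparison.** "Student's t-test or non-parametric (Mann-Whitney) tests, depending on whether the genes" "mRNA expression and protein present or not a normal distribution, will be used to compare" liraglutide with placebo. No normality test or threshold is named.
- **Adjustment.** "Continuous variables will be considered as age-adjusted, sex-adjusted and" "weight-adjusted means with their SDs or median, if values are skewed". No model is given, and no time point for weight. No adjustment is described for medians.
- **Scale.** Expression values will be log-"transformed prior to statistical analyses unless they will be normally distributed".
- **Other methods.** Univariate regressions relate clinical variables to expression. For patients treated for less than 12 weeks the gene analysis is to be adjusted for time, without a stated method. Neither gives an age-, sex- and weight-adjusted treatment test.

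Weight is one of the anthropometric measures (Anthropometrics and Clinical measures), which are taken at baseline and again before surgery (Study Timetable). The background says liraglutide causes modest weight loss, and the section on short-term effects states: "The LEAD trials showed a decrease in mean weight ranging from 1 to 3.2 kg", over 26 or 52 weeks. Innovation says that shorter treatment in some "patients may actually rule out the potential confounding effect of the liraglutide-associated" weight loss.

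**The concern.** A t-test or Mann-Whitney test compares raw groups. It takes no covariates and returns no adjusted mean. A results table following this text would set an adjusted difference beside a p-value from another analysis, and the two can point different ways in a trial of 20 per arm.

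The scale and test rules also collide. One sentence answers non-normality with a log transform, the other with a rank test, and no order is stated. Two analysts could follow the plan faithfully and report different primary results.

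Finally, weight is recorded both before and after treatment. Weight lost because of the drug is a consequence of randomised treatment, not a confounder, so adjusting for it changes the effect being estimated. Because the protocol describes that loss as potentially confounding, the covariate should not be left open.

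**Working it through.** **1. The plan's own figure.** Inputs: 20 per arm, CV 42%, a 33% difference, two-sided alpha 0.05, 90% power (Power Analysis). The log-scale SD is sqrt(ln(1 + 0.42²)) = 0.403.

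- 33% as a reduction: −ln 0.67 = 0.400, and 0.400/0.403 = 0.994 SD. The normal formula needs 22 per arm for 90% and gives 88.1% at 20; the exact t gives 86.5%. This roughly reproduces the plan.
- 33% as a 1.33-fold difference: ln 1.33 = 0.285, or 0.708 SD. This needs 42 per arm; the exact t gives 58.7% at 20.

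Both readings are carried forward, because the plan glosses 33% as about 1.3-fold.

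**2. How often the two analyses disagree.** Simulation, 3,000 trials per setting, 20 per arm, log expression with SD 0.403. Assumptions not in the documents: baseline weight SD 15 kg, its correlation with log expression 0.3, age and sex unrelated to expression. Unadjusted t-test against a linear model with baseline age, sex and weight, at p < 0.05:

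| True log difference | Trials with opposite verdicts |
|---|---|
| −0.40 | 7.5% |
| −0.285 | 13.4% |

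**3. Shift if weight at surgery were the covariate.** Shift = r × SD(log expression) / SD(weight) × arm difference in weight. With r = 0.3 and SD(weight) = 15 kg, this is 0.3 × 0.403 / 15 = 0.00806 per kg.

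- 1 kg: 0.0081 / 0.400 = 2.0% of the target.
- 3.2 kg: 0.0258 / 0.400 = 6.4% of the target.

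The simulation agrees. With a 2.85 kg drug effect on weight, the mean estimate moved from −0.394 to −0.373 and from −0.281 to −0.259. With no true effect it was +0.024, against +0.002 unadjusted.

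**4. If weight change were the covariate.** If half the effect ran through weight change, the estimate fell from −0.398 to −0.195 and power from 76% to 24%. If none did, the estimate barely moved (−0.394 to −0.393), but power fell from 85.7% to 74.1%, because weight change overlaps with arm.

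**5. Power of a single adjusted model.** Noncentral t, 38 − 3 = 35 df, standardised effect divided by sqrt(1 − R²). R² is assumed, since the documents give none.

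| | Unadjusted t | R² = 0 | R² = 0.1 | R² = 0.2 |
|---|---|---|---|---|
| 33% reduction | 86.5% | 86.3% | 89.6% | 92.7% |
| 1.33-fold | 58.7% | 58.5% | 63.1% | 68.2% |

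**The case against.** The adjusted-means sentence can be read as a reporting convention, with the tests left unadjusted on purpose, or as adjustment carried out before testing. The wording allows both. Under the first reading the mismatch between estimate and p-value remains; under the second the method of adjustment is missing.

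Several stronger readings are tempting, and the documents do not support them.

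- **That the plan adjusts for on-treatment weight.** It does not say so. Baseline weight is an equally natural reading. The remarks about confounding by weight loss concern treatment length and actions to equalise weight loss (Innovation, Study Rationale), not a covariate.
- **That the bias would be large.** The large figures need weight change as covariate, which the plan never names. For weight itself the shift is small, and the 1 to 3.2 kg range may overstate the arm difference: it is a decrease over 26 or 52 weeks, whereas treatment here lasts 3 to 12 weeks and both arms follow a supervised diet.
- **That choosing the test on normality inflates false positives.** One sequential version of the rule (raw t, then log t, then Mann-Whitney, checking each arm), on log-normal data with CV 42%, gave 5.1% against 4.7% for a fixed log t-test, with 86.9% power for both. That is negligible.
- **That the markers would end up on incompatible scales.** They could differ, but how often depends on the correlation between mRNA and protein of two cytokines in the same tissue, which is unknown. The plan combines no markers.
- **That a rank test rules out any ratio estimate.** A Hodges-Lehmann shift on log values supplies one, although the plan does not mention it.

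**Conclusion.** The point holds as a gap in specification. The primary comparison has no single analysis that yields both its estimate and its p-value, no stated order between log transformation and rank testing, and no time point for weight. That the adjusted estimate and the p-value would come from different analyses follows from the text, unless an unstated adjustment precedes the test. A changed verdict at 0.05 is only sometimes the result: 7.5% to 13.4% of simulated trials, assuming correlation 0.3 and weight SD 15 kg. Adjustment for weight at surgery is possible, not established; under the same assumptions and a 1 to 3.2 kg arm difference it would shift the estimate by about 2% to 6% of the log target. A serious distortion arises only if weight change were used and part of the effect ran through it. The point does not rest on the sample size calculation. It is worth correcting because a better-defined analysis is available at almost no cost.

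**What to change.** Amend Statistical Considerations as follows.

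- For each marker, make one linear model on log expression the primary analysis, with arm, baseline age, sex and baseline (pre-randomisation) weight. Fix the log scale in advance, whatever a normality check shows.
- Report the adjusted liraglutide/placebo ratio, its 95% confidence interval and its p-value, all from that model.
- State that weight measured after randomisation, and weight change, are not covariates in the primary model.
- Keep Mann-Whitney as a sensitivity check.
- State how the time-adjustment rule for patients treated for less than 12 weeks fits with this model: whether treatment duration enters it and in what form, or is handled separately.

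The cost is wording and three degrees of freedom, about 0.2 points of power if the covariates explain nothing. With an assumed R² of 0.1 to 0.2, power rises from 86.5% to about 90–93% if 33% is a reduction on the log scale, or from about 59% to 63–68% if it is a 1.33-fold difference. The plan already names all three covariates, so no new data collection is needed.

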572 **Subject Compliance**

573 We estimate that the majority of the participants who will be considered eligible will
574 complete the study. Attrition can be estimated as lower than 10%. In the event that
575 participants are lost to follow-up, the research coordinator will contact with the study
576 participant by telephone. The research coordinator will be trained in effective telephone
577 technique to maximize recruitment success. All groups will receive lifestyle and diabetes
578 education, as part of the standard care, to insure similar glycemic control between arms.
579 Study patients will be advised to monitor their capillary glucose twice daily, fasting in the
580 morning and post-prandially. Glucose profile will be tracked bi-weekly by the research
581 coordinator by email or telephone.

582

583 **Statistical Considerations**

584 POWER ANALYSIS

585 The statistical power (two-sided, $\alpha=0.05$) of the study was calculated to detect statistically
586 and clinically meaningful differences in the primary endpoint between the two study arms.
587 Our preliminary data showed that EAT inflammatory genes, including IL-6 and TNF- α are
588 upregulated in subjects with T2DM and CAD and higher in EAT as compared to SAT⁴⁻¹⁷.
589 From our recently published study, we calculated the average coefficient of variance (CV)
590 for differential inflammatory genes to be 42%, but for only 5 T2DM patients.¹⁷ As there
591 are no data on the effects of liraglutide on EAT inflammation, the power analysis was based
592 on our previous data and on the assumption that the difference in EAT TNF- α and IL-6
593 expression between liraglutide treated and placebo treated patients would be clinically
594 meaningful at 33% (approx. 1.3X fold). Based on these data, we propose to sample 40
595 individuals. There will be 20 on liraglutide plus standard therapy versus 20 subjects on
596 liraglutide-matching placebo plus standard therapy contributing EAT and SAT samples
597 collected during cardiac surgery. Using the power set at 90% and $\alpha=0.05$, and given the
598 CV of 42%, this sample size will provide adequate power to detect the clinically significant
599 expected difference (33%) in EAT TNF- α and IL-6 between the two study arms.

600 Based on pre-existing data, this sample size will provide adequate power to detect
601 statistically significant differences in EAT TNF- α and IL-6 between the two study arms in

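### The univariate regressions of EAT expression on EAT thickness carry no treatment term; if the arms are pooled and post-treatment thickness is used, drug effects on both can induce a correlation.

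*Combined protocol and SAP*

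**What the plan says.** The closing paragraphs of Statistical Considerations give the whole specification: "Univariate regression models will be performed to assess the correlation between clinical" "variables, including echocardiographic EAT thickness and blood tests, and EAT gene and" "protein expression. Two-tailed $p < 0.05$ indicates statistical significance". That is one predictor per model, so treatment is not in it.

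Nothing elsewhere adds a treatment term, a by-arm analysis or a placebo-only analysis. Two adjustments are named. The first concerns how means are presented: "treatments. Continuous variables will be considered as age-adjusted, sex-adjusted and" weight-adjusted. The second is an unspecified time adjustment of the gene analysis for patients who do not complete 12 weeks.

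The plan is silent on two points that matter here: whether the arms are pooled, and whether baseline thickness, pre-surgery thickness or its change is the predictor. Under Visit Procedures, thickness is measured at baseline and again before surgery, and adipose tissue is collected only during surgery. Expression is therefore always a post-treatment value.

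**The concern.** Randomised treatment is expected to move both variables in the same direction. The power section expects expression to differ by 33% between arms and thickness to differ by 20% to 30%. When both arms enter one regression without a treatment term, the slope mixes the gap between arms with the association among patients on the same treatment. If the second is zero, the first still tilts the line.

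What is at stake is interpretation. A significant slope would invite the reading that a patient's echocardiographic thickness reflects the inflammatory state of that patient's epicardial fat. Under the plan's own expected effects, such a slope could appear several times more often than the nominal 5% with no such link within either arm.

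**Working it through.** **Inputs, all from Statistical Considerations unless noted**

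- Allocation: "individuals. There will be 20 on liraglutide plus standard therapy versus 20 subjects on" placebo, so n = 20 per arm and N = 40.
- Expression: CV 42% and an arm difference of 33%, also described as about 1.3-fold.
- Thickness: 9.6 mm with SD 2; expected differences of 20% (1.92 mm) and 30% (2.88 mm).
- Test: two-sided 5%.
- Assumed, not in the documents: zero within-arm correlation, normal errors, equal SDs in the two arms, and the stated thickness effects taken as differences between arms.

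**Step 1. Standardised differences, checked against the plan's own power**

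The plan gives no figure for the regressions. Its power statement ("collected during cardiac surgery. Using the power set at 90% and" two-sided 5%; "CV of 42%, this sample size will provide adequate power to detect the clinically significant" "expected difference (33%) in EAT") fixes the expression effect, but not the scale. With power ≈ Φ(d√(n/2) − 1.96) and n = 20:

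- Log scale, ratio 0.67: SD = √ln(1 + 0.42²) = 0.403, d = ln(1/0.67)/0.403 = 0.99, power 88%. This is the closest to the stated 90%.
- Raw scale: d = 0.33/0.42 = 0.79, power 70%.
- 1.3-fold on the log scale: d = ln(1.3)/0.403 = 0.65, power 54%.

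All three are carried forward, because the text supports each of them. For thickness, d = 1.92/2 = 0.96 (power 86%, stated as at least 80%) and d = 2.88/2 = 1.44 (power 99.5%, stated as above 99%).

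**Step 2. Correlation induced by pooling**

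With 1:1 arms and no within-arm correlation,

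ρ = (d₁d₂/4) / √[(1 + d₁²/4)(1 + d₂²/4)],

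where d₁ is the thickness effect and d₂ the expression effect. For d₁ = 0.96 and d₂ = 0.99, ρ = 0.19.

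**Step 3. Rejection rates**

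These come from 400,000 simulated trials per row. The mean sample r runs slightly above ρ.

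| Thickness effect | Expression d | ρ | Mean r | p<0.05, pooled univariate | p<0.05, arm in model |
|---|---|---|---|---|---|
| 20% | 0.65 | 0.13 | 0.14 | 13% | 5% |
| 20% | 0.79 | 0.16 | 0.16 | 17% | 5% |
| 20% | 0.99 | 0.19 | 0.20 | 23% | 5% |
| 30% | 0.65 | 0.18 | 0.18 | 20% | 5% |
| 30% | 0.79 | 0.21 | 0.22 | 27% | 5% |
| 30% | 0.99 | 0.26 | 0.26 | 38% | 5% |
| none (baseline thickness) | any of the three | 0 | 0 | 5% | 5% |

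**Step 4. Sensitivity**

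- The 15% thickness effect anticipated at 3 weeks (d = 0.72), combined with the full expression effect, gives 10% to 15%. The plan describes the 3-week expression difference as about one-fold. If that is a ratio, it means no difference, and the rate is 5%.
- With 18 per arm, to reflect attrition just under 10%, and expression d of 0.79 to 0.99, the rates are 15% to 21% (20% effect) and 25% to 35% (30% effect).
- The plan expects the thickness SD to fall to about 1.5. Applying that to the liraglutide arm only gives 15% to 27% (20% effect) and 23% to 44% (30% effect), so equal SDs do not exaggerate the result.

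**The case against.** The case on the other side has real force.

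- **Pooling is inferred.** A reader might conclude that the plan specifies pooled models. It does not; by-arm analysis is neither planned nor excluded. One model per variable with no restriction by arm is the natural reading, but it remains a reading.
- **The time point is open.** With baseline thickness, randomisation removes the effect in expectation. The problem needs pre-surgery thickness or its change.
- **The correlation is real in the marginal sense.** A reader might say that the regressions will create a correlation where none exists. That goes too far: the pooled association would exist and would be due to treatment. It is also modest, and in every scenario under the main assumptions most trials of 40 would still miss p<0.05. Calling a rejection a false positive is right only if it is read as an association within arms.
- **No stated aim depends on it.** A reader might take thickness tracking inflammation to be a declared rationale. Study Rationale lists that EAT is an inflammatory depot, that liraglutide reduces its thickness, and that it expresses GLP-1R. No objective, hypothesis or endpoint concerns a correlation between thickness and expression.
- **The between-arm thickness effect may be smaller.** One sentence in the power section describes the 20% as a change before and after liraglutide, and both arms receive a supervised low-calorie diet. A smaller gap between arms would induce less.

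All of this limits the size and certainty of the point. None of it supplies a treatment term, and the first two items are themselves choices that the plan needs to state.

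**Conclusion.** The point holds in conditional form. The planned models cannot separate a treatment effect on two variables from an association between them. If the arms are pooled and the thickness value is post-treatment, the nominal 5% becomes about 13% to 23% at a 20% thickness effect and 20% to 38% at 30%, with no within-arm association. This rests on 20 per arm, normal errors, equal SDs, and the plan's expected effects holding as differences between arms. If either condition fails, or if the drug does not move expression, the excess disappears in expectation.

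The consequence is limited to how a supportive, mechanistic correlation is read. A reader should not infer that the primary or secondary treatment comparisons are compromised; they do not use these models. The change is worth making because it is cheap and must precede the analysis to be credible.

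**What to change.** In Statistical Considerations:

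1. State the analysis set, and state which thickness value enters each regression: baseline, pre-surgery or change.
2. In every regression with a post-treatment predictor (pre-surgery thickness, its change, or follow-up blood tests), include treatment arm. Include treatment duration too: it ranges from 3 to 12 weeks and could drive both variables within the liraglutide arm.
3. Report the arm-adjusted slope with its confidence interval. This slope assumes a common association in both arms, so show the two within-arm estimates beside it as description.
4. Keep pooled univariate models for baseline predictors only.

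The cost is one or two degrees of freedom per model and slightly less precision. No new data are needed, and the primary analysis does not change.
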